5.5.8 Prohibited medication

Use of the treatments displayed in [Table 5-1](#) and [Table 5-2](#) is NOT allowed after baseline.

No other treatments for psoriasis than the study treatments and the additional use of calcipotriol 50 µg/g and betamethasone 0.5 mg/g during the first 4 weeks in Arm B1 will be allowed during the Treatment Epoch. Bland emollients and topical glucocorticosteroid treatments of mild to moderate potency on the face, scalp, and/or genitoanal area for Arm A1, Arm A2, Arm B1, Arm C1, and Arm C2 are an exception. Exposure to UV light (e.g., sunbathing and/or the use of tanning devices) other than nb-UVB within the study, from enrollment to Week 104 of the study should be limited. Mild to moderate potency topical glucocorticosteroids will be allowed during the Follow-up Epoch.

Table 5-1 Prohibited treatment (Arm A1, Arm A2 and Arm B1)

Prohibited treatments ^{a, b}	Washout period (before baseline)
Secukinumab	No prior use allowed
Any biologic drug directly targeting IL-17A or the IL-17 receptor (other than secukinumab, e.g., brodalumab, ixekizumab)	No prior use allowed
Alefacept, briakinumab, efalizumab	No prior use allowed
Biological immunomodulatory agents other than the above listed (e.g., adalimumab, etanercept, infliximab)	No prior use allowed
Other systemic immunomodulatory treatments ^c (e.g., methotrexate, cyclosporine A, glucocorticosteroids [oral, i.v., intramuscular, s.c., intra-articular, transdermal], cyclophosphamide) and any treatment for psoriatic arthritis, except for NSAIDs	No prior use allowed
Any biologic drug directly targeting IL-12/IL-23 other than ustekinumab or IL-23 (e.g., guselkumab, tildrakizumab)	No prior use allowed
Other systemic psoriasis treatments (e.g., retinoids, fumarates, apremilast)	No prior use allowed
Photo-chemotherapy (e.g., psoralen plus UVA [PUVA]) or phototherapy ^d	No prior use allowed
Topical treatment that is likely to impact signs and symptoms of psoriasis (e.g., vitamin D analogues, pimecrolimus, retinoids, Salicyl-Vaseline, salicylic acid, lactic acid, tacrolimus, tar, urea, α -hydroxy or fruit acids) ^e	2 weeks
Live virus vaccinations	6 weeks
Any investigational treatment or participation in any interventional study	4 weeks or 5 half-lives (whichever is longer)

NSAID = nonsteroidal anti-inflammatory drug, UVA = ultraviolet light A

a) If the prohibited treatment is used during the study for any indication, patients must discontinue its use if they wish to continue in the study

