5.6.2 Discontinuation of study treatment

Discontinuation of study treatment for a patient occurs when study treatment is stopped earlier than planned in the protocol, and can be initiated by either the patient or the investigator.

Study treatment must be discontinued under the following circumstances:

- Patient wish
- Pregnancy (see [Section 6.5.6](#) and [Section 7.6](#))
- Use of prohibited treatment (see [Table 5-1](#))
- Any other protocol deviation that results in a significant risk to the patient's safety
- Any laboratory abnormalities that in the judgment of the investigator, taking into consideration the patient's overall status, prevents the patient from continuing participation in the study
- The investigator believes that patient's continuation in the study would negatively impact the risk/benefit balance of study participation

Patients who discontinue study treatment should NOT be considered withdrawn from the study. They should return for the assessments indicated in [Table 6-1](#), [Table 6-2](#), and [Table 6-3](#), undergo an EOS visit, and then be discontinued from the study. If they fail to return for these assessments for unknown reasons, every effort (e.g., telephone, e-mail or letter) should be made to contact them as specified in [Section 5.6.3](#).

The investigator must also contact the IRT to register the patient's discontinuation from treatment.

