5.6.6 Discontinuation during the Follow-up Epoch

During the Follow-up Epoch, patients must be discontinued from the study under the following circumstances:

- Patient wish
- Pregnancy (see [Section 6.5.6](#))
- Use of prohibited treatment
- Any other protocol deviation that results in a significant risk to the patient's safety

- Occurrence of relapse

6 Visit schedule and assessments

Table 6-1, Table 6-2, and Table 6-3 list all of the assessments and indicates with an “X” the visits when they will be performed. An “S” indicates that the data for that assessment are to be recorded in the source documents at the site.

[figure not shown]
Patients should be seen for all visits on the designated day or as closely as possible to the originally planned visit. Missed or rescheduled visits should not lead to automatic discontinuation and will be discussed on an individual basis. The investigator and the patient can also request an unscheduled visit whenever necessary, especially during the treatment-free Follow-up Epoch where a worsening of symptoms and quality of life could occur, the investigator should remind the patient of this option.

Patients who prematurely discontinue the study for any reason should be scheduled for an EOS visit as soon as possible, at which time all of the assessments listed for the final visit (EOS) will be performed before any new treatment is initiated. All dispensed investigational product should be reconciled and the AEs and concomitant medications reconciled on the CRF.

At a minimum, patients will be contacted for safety evaluations during the 30 days following the last study visit or following the last administration of study treatment (see Section 5.6.1). Attempts to contact the patient should be recorded in the source documentation.

Table 6-1 Assessment schedule: Screening Epoch and Treatment Epoch (all arms)

	SE	Treatment Epoch																	
Visit number	SC ^a	1							2		3			4				5 ^b	U
Time (weeks)		B	1	2	3	4	8	12	16	20	24	28	32	36	40	44	48	52	
Secukinumab administration at the site		X							X		X			X					
Secukinumab administration at home			X	X	X	X	X	X		X		X	X		X	X	X		
nb-UVB (Arm B1)		One or 2 cycles (of 12-week duration each)																	
Informed consent	X																		
Provide patient diary		S																	
Inclusion/exclusion criteria	X	X																	
Randomization		X																	
Demographics	X																		
Medical history	X	X																	
Vital signs	X	X							X		X			X				X	X

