9.4.2 Statistical model, hypothesis, and method of analysis

For the primary analysis, the following hypothesis testing will be performed:

$$H_{01}: p_{sec} = p_{nbUVB} \text{ versus } H_{A1}: p_{sec} > p_{nbUVB}$$

where p_{sec} and p_{nbUVB} are the proportion of PASI 90 responders in the secukinumab 300 mg s.c. (Arm A1) and nb-UVB (Arm B1) groups, respectively.

The primary analysis method for PASI 90 response at Week 52 will use a logistic regression model with treatment as an explanatory variable and significant covariates among baseline PASI score, age, and body mass index. The best subset of the significant covariates will be selected using a forward selection method based on the likelihood ratio test. Interaction terms will also be considered, if significant, among the best subset of selected covariates and the treatment term.

Statistical significance will be evaluated at a 1-sided alpha level of 0.025. The estimated adjusted odds ratio for Arm A1 versus Arm B1 will be displayed along with the associated 2-sided 95% confidence interval (equivalent to the 1-sided 97.5% confidence interval) and p-value.

If there are issues related to the convergence of the logistic regression model, the above hypothesis will be tested using a Wald test.

The primary analysis is not expected to be influenced by the use of topical treatment within the first 4 weeks since, any effect will be worn off by Week 52.

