9.8 Sample size calculation

The sample size calculation is performed for the primary endpoint (proportion of PASI 90 responders at Week 52) and the key secondary endpoint (proportion of all randomized patients

who achieve PASI 90 response at Week 104, see [Section 9.9](#)). The selected total sample size is 160 patients, such that 80 patients are randomized in each arm.

The sample size calculation based on the proportion of PASI 90 responders at Week 104 was performed using PASS 11.

The power calculations for the primary endpoint are based on the asymptotic Wald test to compare secukinumab 300 mg s.c. versus nb-UVB using the hierarchical method to adjust for multiplicity. Based on data (unpublished) and experiences from recent studies, it is assumed that the proportion of PASI 90 responders at Week 52 will be around 70% after early treatment with secukinumab 300 mg s.c. (Arm A1) and around 35% after 1 or 2 cycles of nb-UVB treatment (Arm B1). With assumed approximate 0% dropout rate in Arm A1, and 20% in Arm B1 until Week 52 due to lack of efficacy or AEs (considered non-responders), the response rate would change to 70% and 28%, respectively. Assuming an absolute difference of 42% in the proportion of patients achieving PASI 90 at Week 52, the sample size of 80 patients in each arm would provide 99.9% power at the 1-sided significance level of 0.025 using asymptotic Wald test for equality of proportions (using PASS 11).

For the Mechanistic Sub-study, additional 12 randomized patients will be treated for 104 weeks with secukinumab 300 mg s.c. (Arm A2), along with 12 patients each from Arm A1b and Arm B1b, and will serve as active groups. Further, 12 patients identified with chronic plaque psoriasis will be allocated to secukinumab 300 mg s.c. for 52 weeks (Arm C1) and another 12 patients with chronic plaque psoriasis will be treated during 104 weeks with secukinumab 300 mg s.c. (Arm C2), both serving as control groups for the Mechanistic Sub-study. As the Mechanistic Sub-study will not involve any formal testing of hypothesis, the sample size for it is obtained in an illustrative manner.

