2.5.3 Handling of missing values/censoring/discontinuations

Missing data will be handled with a modified multiple imputation method. Subjects who discontinued the study before Week 52 because of lack of efficacy or AEs will be considered non-responders. Missing values for other reasons will be inserted by means of the multiple imputation method.

The multiple imputation method is a simulation-based approach where missing values are replaced by multiple Bayesian draws from the conditional distribution of missing data given the observed data and covariates (i.e., under the assumptions of missing at random (MAR)), creating multiple completed data sets, which can then be analyzed using standard methods. [Rubin \(1987\)](#) presented rules how to combine the multiple sets of estimates to produce overall estimates and confidence intervals that adequately incorporate missing data uncertainty.

Missing values for the “change from Baseline PASI score” will be imputed simultaneously based on an underlying normal distribution and using the data augmentation procedure of Markov Chain Monte Carlo (MCMC) method. The change from Baseline in PASI score appears to follow closer to a normal distribution than the actual PASI score. The imputations will be done separately for each treatment group (Arm A1 and Arm B1). For Arm A1 and B1, the imputation will also include Baseline PASI score, age, Baseline BMI as additional variable.

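### The protocol's rules on prohibited-treatment use conflict, and the PASI 90 analysis has no rule for patients who start another psoriasis therapy; this matters mainly at Week 104

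*Protocol*

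**What the plan says.** **Consequence of use.** Protocol Section 5.5.8, footnote a to Tables 5-1 and 5-2, covers use for any indication at any time in the study: "patients must discontinue its use if they wish to continue in the study". Footnote b ties stopping study treatment to undue safety risk and leaves it to the site's discretion; only a live virus vaccination in a secukinumab patient makes it compulsory. Section 5.6.2 lists use of prohibited treatment under "Study treatment must be discontinued under the following circumstances", and adds that such patients are not withdrawn and should return for assessments. Section 5.6.6 lists the same use under "patients must be discontinued from the study under the following circumstances".

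**Consequence for PASI 90.** At Week 52 (Protocol 9.4.3, SAP 2.5.3), patients who discontinue for lack of efficacy or adverse events are non-responders. For everyone else, "Missing values for other reasons will be inserted by means of the multiple imputation method". At Week 104 (Protocol 9.5.1, SAP 2.6.2 and 2.6.3), relapse and failure to reach PASI 50 at Week 52 are added to the non-response list. Prohibited treatment appears in neither list. The imputation assumes missing at random, runs separately by arm, and uses baseline PASI, age, BMI and the changes from baseline in PASI.

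**The concern.** There are two problems. First, sites can follow different passages for the same event, so who leaves, when, and with what recorded reason may vary by site in an open-label trial. Second, the PASI 90 outcome then depends on that recorded reason. A patient who starts another psoriasis therapy is a non-responder if the exit is coded as lack of efficacy, but is imputed if it is coded as prohibited treatment. If the patient stays under assessment, the PASI measured after the other therapy is taken at face value. Either route may count as a responder someone whose control was not achieved by the assigned treatment.

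What is at stake is the meaning of the response rates. It is also the robustness of the Week 104 comparison, which is tested at 1-sided 2.5% in the hierarchy and expects few responders.

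**Working it through.** **1. Which passages conflict**

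| Question | One place | Another place | Compatible? |
|---|---|---|---|
| Stay in the study, Follow-up Epoch? | Footnote a: yes, if use stops | 5.6.6: no | No |
| Stop study treatment? | Footnote b: discretionary, except live vaccine | 5.6.2: mandatory | No |
| Stay in the study, Treatment Epoch? | Footnote a: yes, if use stops | 5.6.2: not withdrawn, assessments continue | Yes |

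**2. What happens to PASI**

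- *Week 52.* Section 5.6.2 keeps patients under assessment, so PASI is likely to be observed and used as is. If it is missing, it is imputed. (5.6.2 also mentions an EOS visit and then discontinuation, so its timing is not fully clear.)
- *Week 104.* Section 5.6.6 forces exit, so PASI is normally missing. Unless the patient has relapsed or was below PASI 50 at Week 52, or the exit is coded as lack of efficacy or an adverse event, it is imputed.

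**3. The plan's own figures**

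Inputs from Protocol 9.4.2 and 9.8: "Statistical significance will be evaluated at a 1-sided alpha level of 0.025"; "the sample size of 80 patients in each arm would provide 99.9% power at the 1-sided significance level of 0.025"; "With assumed approximate 0% dropout rate in Arm A1, and 20% in Arm B1 until Week 52 due to lack of efficacy or AEs"; "the response rate would change to 70% and 28%, respectively".

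Power = Φ{[(p1 − p2) − 1.96·√(2p̄(1 − p̄)/n)] / √(p1(1 − p1)/n + p2(1 − p2)/n)}, with p̄ = (p1 + p2)/2.

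For p1 = 0.70, p2 = 0.35 × 0.80 = 0.28 and n = 80: Φ[(0.42 − 0.1549)/0.0717] = Φ(3.70) = 0.9999. The stated 99.9% is reproduced.

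Key secondary (Protocol 9.9): 0.23 × 0.93 = 0.214 and 0.05 × 0.84 = 0.042, stated as 21% and 4%. Exact enumeration of the 1-sided Fisher test with 80 per arm gives 90.0%, against a stated value of around 89%. Expected responders are 0.21 × 80 = 16.8 and 0.04 × 80 = 3.2.

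**4. Effect of imputing instead of counting as non-response**

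The documents give neither the share q of an arm that leaves for prohibited treatment nor the mean imputed response probability r. Both are assumed. Rate used = planning rate + q × r; r = 0 returns the planning rates.

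*Week 52, patients credited in Arm B1 only (the direction that lowers power):*

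| q | r | Responders added (80·q·r) | B1 rate | Difference | Power |
|---|---|---|---|---|---|
| 5% | 0.35 | 1.4 | 29.75% | 40.25 points | 99.97% |
| 20% | 0.35 | 5.6 | 35% | 35 points | 99.6% |

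The second row credits the whole 20% dropout assumed for B1.

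*Week 104, Fisher's exact test:*

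| q in A1 | q in B1 | r in A1 / B1 | Rates | Power |
|---|---|---|---|---|
| 0 | 0 | – | 21% v 4% | 90.0% |
| 5% | 5% | 0.23 / 0.05 | 22.2% v 4.3% | 91.7% |
| 7% | 0 | 0.23 / – | 22.6% v 4% | 93.8% |
| 7% | 0 | 0.50 / – | 24.5% v 4% | 96.6% |
| 0 | 16% | – / 0.05 | 21% v 4.8% | 85.0% |
| 0 | 16% | – / 0.20 | 21% v 7.2% | 65.4% |

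**5. How much one patient matters at Week 104**

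1-sided Fisher p with 80 per arm: 17 v 3 gives 0.0007; 11 v 3 gives 0.023; 10 v 3 gives 0.040. At the planned effect one patient changes nothing. If the effect is smaller than planned, one patient can decide the test.

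These are simple two-proportion tests, not the full covariate-adjusted imputation analysis.

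**The case against.** A reader might infer that the plan credits treatment failures with responses and so inflates the secukinumab advantage. For example, four such patients per arm, imputed at 0.70 and 0.35, would add 2.8 and 1.4 responders and widen the difference by 1.4/80 = 1.75 points. The documents do not support that reading:

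- 0.70 and 0.35 are arm-average planning rates. The imputation uses each patient's own earlier PASI changes, so a patient losing control would probably receive a lower probability.
- Equal counts per arm are an assumption. Planned dropout for lack of efficacy or adverse events is 0% in A1 and 20% in B1 to Week 52; with relapse included it is 7% and 16% before Week 104. If leavers followed that pattern, crediting them would mainly raise the control rate. Four in B1 alone would narrow the difference by the same 1.75 points.
- Not every user is a failure. Footnote a covers any indication, and Table 5-1 includes live vaccines and systemic glucocorticosteroids. A true failure may be recorded as lack of efficacy or relapse, both already non-response where they apply.

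A reader might also infer that footnote a contradicts 5.6.2 directly. It does not: one concerns staying in the study, the other stopping study treatment.

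Safeguards exist. SAP 2.5.4 plans non-responder imputation, a tipping-point analysis and last observation carried forward for Week 52. It also repeats tables and graphs with non-responder imputation up to Week 104. Protocol Section 6 asks for the EOS assessment before any new treatment starts, so some failures will be detected as relapse.

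All of this limits the size of the problem. It does not close the gap: non-responder imputation acts only on missing values and leaves a PASI observed after another therapy untouched, and SAP 2.6.3 names no missing-data sensitivity analysis for the Week 104 test.

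**Conclusion.** Both parts hold. The follow-up rule (footnote a against 5.6.6) and the study-treatment rule (footnote b against 5.6.2) are contradictory and must be reconciled; no view is taken here on which is right. The analysis rules leave PASI 90 after a prohibited psoriasis treatment to imputation when missing and to face value when observed.

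The primary conclusion is not at risk. The Week 104 key secondary is where the gap matters: exit is forced, few responders are expected, and the assumed scenarios move power both up and down from 90%. No bias of known size or direction is shown, because that would need the number of such patients by arm and their earlier PASI course, which the documents do not give. The point should be addressed, but it does not invalidate the plan.

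**What to change.** 1. Reconcile footnotes a and b of Tables 5-1 and 5-2 with Sections 5.6.2 and 5.6.6, so that one event has one stated consequence in each epoch.
2. In SAP 2.5.3 and 2.6.3, count PASI 90 as non-response, whether PASI is missing or observed, when a prohibited treatment was started for psoriasis before the endpoint visit, whatever discontinuation reason is recorded. Identify these patients from the dated concomitant medication and non-drug therapy records, which hold the reason for use (Protocol 5.5.7). Exclude prohibited treatments used for other indications.
3. The Week 52 report has been prepared (SAP 2.14.1) and Week 104 results have been seen (SAP 2.15). Apply the rule as a disclosed sensitivity analysis of both endpoints, with the rationale in the CSR, and leave the planned main analyses unchanged. Report the number of patients affected in each arm.

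The cost is a wording change in the protocol, a short SAP addition, one extra run of two analyses, and slightly lower response rates in those runs.

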5.5.9 Emergency breaking of assigned treatment code

Not applicable.

5.6 Study completion and discontinuation

5.6.1 Study completion and post-study treatment

A patient will be considered to have completed the study when he or she has completed the last visit planned in the protocol.

Patients who have been screened and have a screening visit recorded in the IRT system at the time that the planned enrolment number is met will be allowed to enter the study and be randomized if they are eligible.

The investigator must provide follow-up medical care for all patients who are prematurely withdrawn from the study, or must refer them for appropriate ongoing care.

For all patients a safety follow-up visit should be conducted (e.g., by telephone) 30 days after the last study visit or 12 weeks after the last dose of study treatment, whichever is later. The information to be collected at this follow-up visit includes concomitant medications, AEs, and survival status.

5.6.2 Discontinuation of study treatment

Discontinuation of study treatment for a patient occurs when study treatment is stopped earlier than planned in the protocol, and can be initiated by either the patient or the investigator.

Study treatment must be discontinued under the following circumstances:

- Patient wish
- Pregnancy (see [Section 6.5.6](#) and [Section 7.6](#))
- Use of prohibited treatment (see [Table 5-1](#))
- Any other protocol deviation that results in a significant risk to the patient's safety
- Any laboratory abnormalities that in the judgment of the investigator, taking into consideration the patient's overall status, prevents the patient from continuing participation in the study
- The investigator believes that patient's continuation in the study would negatively impact the risk/benefit balance of study participation

Patients who discontinue study treatment should NOT be considered withdrawn from the study. They should return for the assessments indicated in [Table 6-1](#), [Table 6-2](#), and [Table 6-3](#), undergo an EOS visit, and then be discontinued from the study. If they fail to return for these assessments for unknown reasons, every effort (e.g., telephone, e-mail or letter) should be made to contact them as specified in [Section 5.6.3](#).

The investigator must also contact the IRT to register the patient's discontinuation from treatment.

5.6.3 Withdrawal of consent

Patients may voluntarily withdraw consent to participate in the study for any reason at any time. Withdrawal of consent occurs only when a patient:

- Does not want to participate in the study anymore and
- Does not allow further collection of personal data

In this situation, the investigator should make a reasonable effort (e.g., telephone, e-mail, letter) to understand the primary reason for the patient's decision to withdraw his/her consent and record this information.

Study treatment must be discontinued and no further assessments conducted, and the data that would have been collected at subsequent visits will be considered missing.

Further attempts to contact the patient are not allowed unless safety findings require communicating or follow up.

All efforts should be made to complete the assessments prior to study withdrawal. A final evaluation at the time of the patient's study withdrawal should be made as detailed in [Table 6-1](#), [Table 6-2](#), and [Table 6-3](#).

Novartis will continue to keep and use collected study information (including any data resulting from the analysis of a patient's samples until their time of withdrawal) according to applicable law.

All biological samples not yet analyzed at the time of withdrawal will no longer be used, unless permitted by applicable law. They will be stored according to applicable legal requirements.

Patients who withdraw their consent to participate in the Mechanistic Sub-study, will still be able to participate in the Main Study provided they keep their consent to this part of the study.

